**Computer screen simulation for task:**

[figure not shown]
g. Visit four (menthol smokers only): Participants who report typically smoking menthol cigarettes will be invited to complete a fourth session. Participants will undergo overnight tobacco/nicotine abstinence before the visit ( $eCO \leq 12 \text{ ppm}$ ). Participants will then be randomized 1:1 to e-cigarette flavor order (tobacco e-cigarette, menthol e-cigarette). They will complete a 30-minute ad libitum session with the first product, based on randomization, followed by a 1.5 hour standard washout period, followed by a 30-minute ad libitum vaping session with the second product. Throughout each session, puff topography will be measured via a pressure sensor attached to the e-cigarette device. Participants will complete self-report measures of smoking urges and withdrawal symptoms pre- and post-vaping session. In addition, they will complete measures of subjective vaping experience, perceptions of flavor, product demand, and intentions for

future use. We anticipate that the session will last ~3 hours.

Participants will earn \$50 for attending the study visit.

h. **Six-month follow-up:** Six months after completion of visit 3 (or study discontinuation), participants will be contacted by phone to assess ongoing use of study products. Three attempts will be made to contact the participant for this follow-up. If they endorse ongoing use, they will be advised to quit all tobacco use and offered a referral to the Quitline. We anticipate this phone follow-up to last no more than 10 minutes. This follow-up assessment is for safety monitoring only.

3. Due to COVID-19 and the need to keep patients and researchers safe, we will use Zoom, a HIPAA compliant, university approved video conferencing software, during the visit. This will allow the participant to smoke freely (unmasked) while the researcher can watch and communicate with the participant via video conferencing from outside the clinic room. We will utilize Zoom as much as possible and only enter the room when absolutely necessary.
4. All tests, procedures, and visits are being performed solely for research purposes and are not billable to insurance companies.
5. Samples will be labeled only with a unique study identification number and only members of the research team will have access to the samples. Samples will be disposed of one month after the final report is sent to the Principal Investigator, unless participants agree to have their samples stored for future testing.
6. Timeline/project flow:

Note. +CO ≤ 12 ppm; \*blood draws, topography, self-report measures of craving, withdrawal, and product liking. 6 month follow-up not depicted.

#### F. Risk/benefit assessment:

1. **Physical risk:** The potential risks for this study are minimal. There is a slight risk of discomfort, bruising and infection with blood draw. Blood will be drawn by trained research staff. IVs will be placed by an RN or LPN. Sterile instruments will be used and for blood draws, the participants skin will be cleaned with an alcohol wipe at the site of the needle stick. Participants will complete no more than two study visits in a seven-day period.
2. **Psychological risk:** Risks for participants include those associated with the inconvenience of participation including answering surveys, providing blood samples, and completing multiple visits. To minimize the inconveniences associated with study participation we will review all data collection instruments and study procedures to minimize the number of items in our instruments and improve the accessibility and convenience of our study procedures. We anticipate using several methods to enhance convenience to participants, including providing rideshare services to and from all study visits and offering study visits throughout the day. Another risk is feeling pressured to be in the study, which we will track in order to monitor and will report as

an adverse event. Finally, although very unlikely, some questions may make participants uncomfortable; participants are not required to answer questions they do not wish to.

3. Social risk: None
4. Economic risk: None
5. Potential benefit of participating in the study
  - a. There are no direct benefits to participants for participating in this study
  - b. The researchers hope that the information gathered from this research may be useful in informing regulations to maximize public health

**G. Location where study will be performed:** The screener visit will take place at Swope Health Central, [name], in Kansas, Missouri or at the KUMC CRU in Fairway, Kansas based on the preference of each participant. Study visits 1, 2, and 3 will take place at the KUMC CRU in Fairway, Kansas. All data will be directly entered into an electronic data capture system (i.e., RedCap or CRIS), therefore minimizing the use of paper records. If paper records are generated, they will be stored in locked file cabinets. Only study staff will have access to the locked records and the secure online electronic data capture system.

**H. Collaboration (with another institution, if applicable):** N/A

**I. Single IRB Review for a Multi-site study (if applicable):** N/A

**J. Community-Based Participatory Research (if applicable):** N/A

**L. Assessment of Subject Safety and Development of a Data and Safety Monitoring Plan**

1. The current study does not pose more than minimal risk; however, we are extremely sensitive to the recent cases of acute lung injury associated with e-cigarette products and the CDCs warnings. We continue to closely monitor the situation. To address this concern, we will obtain informed consent, closely monitor AEs and SAEs and promptly report any that occur. [name] will provide medical oversight. In addition, we will have firm stopping rules to protect the safety of study participants. Further, we will purchase our supply directly from JUUL and will advise participants to not modify the e-liquid in any way – e.g., adding THC or vitamin E – which has been the case in the majority of reported cases. Altering the e-liquid would be difficult as participants will be provided JUUL pods which are closed systems, not easily tampered with. We also include a 6-month follow-up to assess for any on-going study product use and again offer a referral to the Quitline.
2. We will protect participants and minimize risks by using the strict exclusion criteria and careful monitoring of AEs. AEs will be tracked during regularly scheduled visits (including 6-month phone follow-up) or through spontaneous reports made by participants. Drs. [name], [name], and [name] will be made aware of unexpected or serious AEs within 24 hours of the first report by participants; all other AEs will be reviewed weekly by Drs. [name] [name] and discussed at regular meetings with [name]. SAEs will be reported to the KUMC IRB within 24 hours of first awareness of the event. Unexpected adverse events that are related to the study products will be reported to KUMC IRB within 5 working days of first awareness of the event if the event is not serious and within 24 hours of first awareness if the event is serious. Unexpected adverse events that are unrelated to the study products will be reported to the KUMC HSC during yearly routine event reporting. [name] will determine relatedness for each reported AE. SAEs will be defined as any event experienced by a study subject while using the study device that is fatal, life-threatening (subject was at risk of death from the event as it occurred), disabling or incapacitating, requires inpatient hospitalization or prolongs a current hospitalization, or required intervention to prevent permanent impairment or damage.
3. In the case of AEs, participants will be reminded of the voluntary nature of the study and be allowed to discontinue participation without negative consequences. In the case of SAEs related to use of study products, participation will be discontinued.

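### Section II.L sorts unexpected adverse events only by relatedness to the study products, so unexpected events caused by study procedures can be left with only a yearly report to the board

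*Combined protocol and SAP*

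**What the plan says.** Section II.L item 2 of the combined protocol and SAP contains three rules on reporting to the board.

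- Serious events, with no condition on cause: "SAEs will be reported to the KUMC IRB within 24 hours of first awareness of the event".
- Unexpected product-related events: "Unexpected adverse events that are related to the study products will be reported to KUMC IRB within 5 working days" if not serious, and within 24 hours if serious.
- Unexpected events not related to a product: "Unexpected adverse events that are unrelated to the study products will be reported to the KUMC HSC during yearly routine event reporting".

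The same item limits what counts as serious by time as well as by outcome: "SAEs will be defined as any event experienced by a study subject while using the study device that is fatal", followed by the other outcomes. It also sets an internal rule, under which the study leads "will be made aware of unexpected or serious AEs within 24 hours of the first report by participants". All other AEs are reviewed internally each week.

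Section II.L item 1 promises that AEs and SAEs will be reported promptly, but gives neither a recipient nor a time.

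Section II.F item 1 describes the physical risk of taking part. The harms it names come from blood collection: "There is a slight risk of discomfort, bruising and infection with blood draw".

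**The concern.** The research can harm a participant in two ways: through a product, or through what is done to study it. Section II.L item 2 asks only about the first. A complication of the catheter or of a blood draw is caused by the research but not by a product, so the wording puts it with events that have nothing to do with the trial.

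At stake is how soon the board hears of it. An unexpected but non-serious catheter problem could recur across participants while the board waits for the annual report, although an equally minor unexpected product effect would reach the IRB within 5 working days. The mismatch stands out because blood collection is the only source of physical harm named in II.F item 1.

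**Working it through.** No power or sample-size figure is involved. The check reads the rules of II.L item 2 as a decision table and places an event caused by the catheter or a blood draw in each cell. Such an event is, by assumption, not related to a study product.

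1. **Unexpected, not serious.** The 24-hour SAE rule does not apply. The rule for product-related events ("Unexpected adverse events that are related to the study products will be reported to KUMC IRB within 5 working days of first awareness") does not apply either. Only the yearly rule is left. The same event caused by a product would be due within 5 working days.
2. **Unexpected, serious, arising while the device is in use.** The SAE definition is met, so the unconditional 24-hour rule applies. The yearly sentence makes no exception for seriousness, so on its wording it applies as well. The two rules overlap without an order of precedence, but a fast route exists.
3. **Unexpected, serious in outcome, arising when the device is not in use** (for example, a serious complication that appears after the visit). The SAE definition is not met because of its device-use clause. Only the yearly rule is left.
4. **Expected, not serious** (arguably the discomfort, bruising and infection listed in II.F item 1). The yearly sentence covers only unexpected events. The plan gives no board timetable here, only weekly internal review.

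Cells 1 and 3 are therefore the gap: the yearly report is the only board route with a stated time.

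**Delay.** A yearly cycle means up to about 12 months, against 5 working days for the comparable product-related event in cell 1.

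**Exposure, for context only.** Section II.C plans 20 participants, and section IV.B gives 5 draws per visit at 3 visits. With one catheter per visit and all visits completed:

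- catheter placements: 20 × 3 = 60
- blood draws: 20 × 3 × 5 = 300
- volume per participant: 7 mL × 5 × 3 = 105 mL, which reproduces the plan's figure

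The draws are taken through the catheter, so 300 draws are not 300 needle sticks. These counts show how often the procedures occur, not how many events would be misrouted. The documents give no event rate from which to estimate that.

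**The case against.** The strongest reply is that the plan already has safeguards that do not depend on the cause of an event. SAEs as defined go to the IRB within 24 hours. The study leads hear of every unexpected or serious event within 24 hours. Item 1 promises prompt reporting, and medical oversight is in place. The team able to act is therefore informed quickly, and only notice to the board is late. This stands, and it limits the point. It does not close the gap: internal notice is not board notice, and the general promise in item 1 sits beside a specific yearly rule that says otherwise.

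A reader might infer several stronger things that the documents do not support.

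- *That reporting speed depends on product-relatedness alone.* Seriousness and expectedness matter too.
- *That the harms named in II.F would go to the yearly report.* Being listed, they are arguably expected, and the yearly sentence covers only unexpected events.
- *That every catheter complication at visit 1 goes to the yearly report because that session uses the participant's own cigarettes.* Expected events are outside the sentence, an event meeting the SAE definition has the 24-hour rule, and section II.B counts the usual-brand cigarette among the products.
- *That the yearly report would arrive after the last catheter was placed.* The documents give no accrual rate or enrolment period, and the spacing of one person's visits does not give the length of the trial.
- *That item 3 of II.L has the same defect.* Its product-only sentence concerns when participation ends, not board reporting, and is no part of this point.

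Item 2 also names both the KUMC IRB and the KUMC HSC without saying whether they are one body. The board's own reporting requirements are not in the documents, so the delay described here is the one the protocol states, not necessarily what would happen in practice.

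**Conclusion.** The point holds in a limited form. As written, II.L item 2 leaves two kinds of unexpected procedure-related event with only a yearly report to the board: non-serious ones, and serious ones that arise when the device is not in use. For the non-serious kind, the contrast is up to about a year against 5 working days for a comparable product-related event.

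This rests on a literal reading of the product-relatedness wording and of the device-use clause, and on treating the IRB and the HSC as the board for this purpose. How many events would be affected is unknown. No endpoint or analysis is touched. It is a stated rule that gives a worse result for safety reporting than the plan's own standard for product effects, and it is cheap to correct.

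**What to change.** In II.L item 2:

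- extend the fast-route sentence to events related to the study products *or study procedures*;
- restrict the yearly sentence to events unrelated to both the study products and the study procedures;
- have the person who judges relatedness record product-relatedness and procedure-relatedness as separate entries;
- reconcile the yearly sentence with the promise of prompt reporting in item 1.

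The first two changes take both kinds of event in the gap off the yearly route. Whether a serious event outside device use is then due in 24 hours or in 5 working days depends on how the device-use clause of the SAE definition is read, so the amendment should state this.

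The cost is a short wording amendment, one extra field on the AE form, and possibly a few more 5-day reports.

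### The SAE definition is tied to time of device use, so some serious events within the AE-tracking window lose the 24-hour IRB report; two reporting deadlines also overlap

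*Combined protocol and SAP*

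**What the plan says.** All the rules are in section II.L of the combined protocol and SAP.

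- **Definition (item 2).** "SAEs will be defined as any event experienced by a study subject while using the study device that is fatal, life-threatening", followed by further outcomes, among them "requires inpatient hospitalization or prolongs a current hospitalization".
- **Tracking window (item 2).** "AEs will be tracked during regularly scheduled visits (including 6-month phone follow-up) or through spontaneous reports made by participants".
- **SAE rule (item 2).** "SAEs will be reported to the KUMC IRB within 24 hours of first awareness of the event".
- **Unexpected and product-related (item 2).** To the IRB in 5 working days "if the event is not serious and within 24 hours of first awareness if the event is serious".
- **Unexpected and not product-related (item 2).** "Unexpected adverse events that are unrelated to the study products will be reported to the KUMC HSC during yearly routine event reporting".
- **Internal notice (item 2).** The study doctors "will be made aware of unexpected or serious AEs within 24 hours of the first report by participants"; other AEs get weekly internal review.
- **General promise (item 1).** The team will "closely monitor AEs and SAEs and promptly report any that occur", with no deadline or recipient named.

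Item 3 attaches discontinuation of participation to product-related SAEs, using the same SAE label. Section II.E item 2h places the phone call six months after visit 3 or discontinuation and gives its purpose as safety monitoring.

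**The concern.** Seriousness is normally a property of the outcome: death, threat to life, hospital admission and so on. Timing relative to exposure bears on relatedness, which item 2 already treats as a separate judgement. Here a timing condition is built into the SAE label itself, and the label decides who is told and how fast. The plan therefore looks for events over about six months but can apply its fastest external report only to those that arise during use.

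At stake is the time to IRB notice for a limited group of serious events. Section IV.E plans no ongoing third-party monitoring, so the IRB and HSC reports are the only outside routes that the supplied text describes. No efficacy endpoint or analysis is affected.

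**Working it through.** There is no planned figure to reproduce. The check applies the item 2 rules to each kind of event that meets a seriousness outcome.

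**Step 1: what the use condition covers.** It can be read in two ways.

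- *Moment of use.* Only onset during puffing counts.
- *Period of use.* Onset at any time while the participant is a user of the product counts. This is the more lenient reading. It fits the home practice in section II.E items 2c and 2e, and the outcome of a prolonged hospital stay, which could hardly arise within a puffing session.

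On the lenient reading two groups are still outside: events that begin after use stops, and events before the product is handed over. Handover follows the randomization at the end of visit 1 (section II.E items 2b and 2c). The second group depends on whether the usual-brand cigarette is a study device. Item 2b speaks of device and product side by side when describing the topography sensor, so it does not settle this.

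**Step 2: the route for a serious event outside the definition.** The word serious in the other sentences may carry its ordinary sense, or it may carry the use condition over from the SAE definition.

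| Event outside the definition | Serious in the ordinary sense | Serious carries the use condition |
|---|---|---|
| Unexpected, related | IRB, 24 hours | IRB, 5 working days |
| Unexpected, unrelated | HSC, yearly | HSC, yearly |
| Expected, related | no stated deadline | no stated deadline |
| Expected, unrelated | no stated deadline | no stated deadline |
| Internal notice | 24 hours for all | 24 hours if unexpected; weekly review if expected |

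Three of the four classes lose the 24-hour IRB report on either sense, and all four on the narrower one. These are counts of event classes, not of events. The yearly sentence names the HSC and the faster ones name the IRB; the supplied text does not say whether these are the same body.

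**Step 3: a concrete case.** At visit 1 a catheter is placed and the usual-brand cigarette is smoked before any take-home product is supplied. Suppose a serious catheter complication arises then, and study device means the e-cigarette or heat-not-burn device. The event is outside the definition. Relatedness in the reporting sentences is to the study products, so it counts as unrelated. If unexpected, it goes to the HSC yearly; if expected, it has no stated deadline. Section II.F item 1 lists infection with blood draw as a slight risk, but nothing says whether a serious complication would be classed as expected.

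**Step 4: a serious event inside the definition.** All four classes are SAEs and go to the IRB within 24 hours. The unexpected, unrelated class also meets the yearly sentence, which makes no exception for serious events. Two deadlines apply to it, and this overlap does not depend on how use is read.

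**The case against.** The strongest reply is that the loss is narrow. With serious in its ordinary sense, an unexpected, product-related serious event still reaches the IRB within 24 hours, so the lung-injury concern in item 1 is most likely covered. Internal 24-hour notice most likely remains for every serious event. Item 1's promise of prompt reporting covers AEs as well as SAEs, so events outside the definition still fall under it. Yearly reporting of unrelated events may be deliberate. The reporting deadline runs from first awareness, and after the visits the only scheduled contact is the 6-month call, so a wider definition would not bring detection forward. The study has 20 participants.

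All of this stands and limits the size of the point. It does not remove it: internal notice goes to the study team, item 1 names no deadline or recipient, and an intention to report unrelated events yearly would still conflict with the 24-hour SAE sentence.

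It is also fair that the catheter case must not be stretched. A reader might infer that study-procedure complications generally fall outside. On the period-of-use reading the condition is temporal, not causal, so a catheter infection that starts during the take-home period is inside the definition.

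**Conclusion.** The point holds, as a drafting fault with a narrow practical effect. Outside the period of use, a serious event that is unexpected and unrelated moves from a 24-hour IRB report to yearly HSC reporting, and an expected one has no stated deadline beyond item 1's general promise. Inside the definition, the unexpected, unrelated SAE is under two conflicting deadlines.

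A reader might infer that nearly all follow-up is unprotected. Two practice gaps of 2 to 5 days, with at most two visits in seven days (section II.F item 1), put visit 3 at 7 to 10 days after visit 1. Taking six months as 183 days, 183/(183 + 10) = 94.8% and 183/(183 + 7) = 96.3% of the time would follow product use if use stopped at visit 3. The documents do not support that as a measure of the problem. They do not say when use stops, the call exists partly to find continuing use, and the share is 0% if use continues to the call. Visit 4 has no stated date. Time shares are not event rates, and no SAE rate is given. Section I.B item 3 reports no serious adverse events in the trials it cites. No frequency or time share is claimed here.

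The size of the effect depends on undefined terms: use, study device, serious and expected. The text between sections II.J and II.L was not available to check.

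**What to change.** In section II.L item 2, for safety reporting:

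1. Remove the clause that ties SAEs to use of the device, so that SAEs are classified by outcome over the AE-tracking window already stated, including events from study procedures. Keep relatedness as a separate judgement, as planned.
2. Reconcile the 24-hour SAE sentence with the yearly sentence for serious unrelated events, and say whether the IRB and the HSC are the same recipient.
3. Reconcile item 3 with the revised definition. Its discontinuation sentence uses the same SAE label, so a wider definition would also widen its reach. No discontinuation rule is proposed here.

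The cost is a short text edit and possibly a few more IRB reports. No visits, samples or staff are added.
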